Services will be provided to clients as part of routine MOH service provision. No adverse events as a result of this study are anticipated. If complications arise during routine service provision, the regular mechanisms will be followed, such as contacting senior providers and initiating referrals. (See Section 4b13).

b. If a Data Safety Monitoring Board (DSMB), or equivalent, will be established, describe the following: **N/A**

- The DSMB membership, affiliation and expertise.
- The charge or charter to the DSMB.
- Plans for providing DSMB reports to the IRB.

c. Describe plans for interim analysis and stopping rules.

13. Plan for reporting unanticipated problems/adverse events:

Describe plan for reporting to the IRB and (if applicable) to the sponsor. Include plan for government-mandated reporting of abuse or illegal activity.

We do not expect any study-related adverse events. See section 12 and 4b13.

Should any adverse event occur in relation to or at the time of the data collection, the data collectors will be trained to notify their team leader immediately by phone, who will notify the co-investigator, [name], the Jhpiego Uganda Country Director. [name] will notify the PI immediately.

If the adverse event is related to the health of the participant, trainers or data collectors will work the health workers to ensure that the participant is attended to as soon as possible, inform the nearest health facility by phone and organize transport for participant and accompanying relative promptly. The trainers or data collectors will inform the facility in-charge. At the same time, the team leader will inform [name] who in turn will liaise with the DCMOs. [name] will consult with the PI. The PI will report any adverse event to the IRB within 3 business days.

14. Other IRBs/Ethics Review Boards:

This study will be reviewed by the institutional review board of the Makerere University School of Public Health in Kampala, Uganda (FWA#00011353).

15. Outside collaborations:

The American Academy of Pediatrics is collaborating with Jhpiego to provide the training and mentoring in immediate newborn care and resuscitation, HBB. They will also provide input on newborn indicators, analysis, and any other newborn related instruments.

Protecting Families Against Aids (PREFA) will hire and manage data collectors for the study with close involvement and oversight by Jhpiego for project management. Our goal is to build the capacity of PREFA for MNH work and for data collection. Jhpiego will adequately train PREFA staff and the data collectors in ethical conduct of research. PREFA will also leverage their relationships within districts in order to introduce the project to the District Health Officers.

Roles and Responsibilities Matrix for IRB Application

Insert Institutions in Collaborator column(s); add additional columns if necessary.

	Jhpiego	Collaborator 1 PREFA	Collaborator 2 AAP
Primary Grant Recipient	Jhpiego		
Subcontractor		Prefa	AAP

For the following, indicate “P” for “Primary”, “S” for “Secondary” as appropriate to role and level of responsibility.) Add additional items if useful.

1	Human subjects research ethics training for data collectors	P	S	S
2	Day to day management and supervision of data collection	P	S	
3	Reporting unanticipated problems to the JHSPH IRB/Sponsor	P	S	S
4	Hiring/supervising people obtaining informed consent and/or collecting data	P	S	

5	Execution of plan for data security/protection of participant data confidentiality, as described in Sect. 5.	P	S	S
6	Biospecimen processing, storage, management, access, and/or future use	n/a		

16. Oversight plan for student studies: Not applicable

17. Oversight plan for studies conducted at non-JHSPH sites, including international venues, for which the JHSPH investigator is the responsible PI:

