Objective 4 (OUTCOMES): Improve and sustain **case management** of PPH and newborn resuscitation during observations of care, as measured by a) percent of women with undelivered placenta after 30 minutes who are

treated with oxytocin, and b) percent PPH cases that receive repeated dose of oxytocin or misoprostol, c) percent of newborns not breathing at birth who are breathing or being ventilated with bag & mask at one minute.

Objective 5 (IMPACT): Reduce over time: a) the percent of facility-based deliveries who experience PPH; b) the PPH-related case fatality rate, and c) the perinatal death rate (the fresh stillbirth rate and early newborn mortality rate at 24 hours or prior to discharge)¹.

Prior to presenting the hypotheses, we describe briefly below the three study arms and three time points of data collection. More description is provided in the Study Procedures section. (See Figure 1, page 11)

Table 1. Brief Description of Three Study Arms/Groups

Arm	Short Name	Component 1	Component 2	Component 3
		Training onsite (BAB, HBB) of providers, simulators left at facility	Peer Practice Coordinator (PPC) is trained and expected to hold weekly onsite practice sessions with providers	Mobile messages remind all trained providers to practice scenarios; and PPC has weekly mobile support from district trainer
1	Training-only	Yes	No	No
2	Partial Package	Yes	Yes	No
3	Full Package	Yes	Yes	Yes

Hypotheses

Overall Hypothesis: The partial package intervention (one-time, onsite training of providers, combined with low-dose, high-frequency peer-led practice sessions) and the full-package intervention (adding reminders and mobile support) will lead to significant gains in provider competencies (between immediately post-intervention to midline) and provider performance of key interventions *BAB* and *in HBB*, which are both maintained once the active intervention ceases.

Specific Hypotheses:

In BAB and in HBB related to the primary outcomes (see Section 4b5):

1. Provider competencies and performance will not decline (i.e. will be non-inferior) between midline and endline in the *full* package group.
2. Provider competencies and performance will not decline (i.e. will be non-inferior) between midline and endline in the *partial* package group.
3. At endline, the provider competency level and the performance level of the *partial* package group will be significantly higher than those of the training-only group.

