4. At endline, the provider competency level and the performance level of the *full* package group will be significantly higher than those of the training-only group.

2. Background and rationale:

Disease Burden: Postpartum Hemorrhage and Neonatal Apnea/Asphyxia

Postpartum hemorrhage (PPH) is the leading cause of maternal mortality worldwide (1), accounting for one-quarter of maternal deaths (2). The global incidence of postpartum hemorrhage has been reported at 10.8%, with a range from 7.2% in Oceania to 25.7% in Africa (3). About one-quarter of global neonatal deaths are due to birth

¹ Note: These rates or proportions may increase between baseline and midline due to better reporting, and we expect these to decrease due to the intervention between midline and endline.

asphyxia and another one million stillbirths occur during the intrapartum period—these stillbirths are often misclassifications of secondary apnea. A large proportion of these two million deaths could be averted with the timely and correct use of neonatal resuscitation (4).

Uganda, the setting for this study, has a maternal mortality ratio of 310/100,000 live births (5) and according to regional estimates, about 34% of these deaths are due to postpartum hemorrhage (6). The national neonatal mortality rate is 29 per 1000 live births and the stillbirth rate is 25/1000 (7). It would be expected that 28% of neonatal deaths would be due to asphyxia/apnea in this setting (6). The proportion of births with a skilled attendant is about 80% in urban areas and 40% in rural areas (7).

Neonatal Asphyxia/Apnea Interventions

The American Academy of Pediatrics and partners developed “Helping Babies Breathe” (HBB) (8), a training package designed to increase newborn survival by improving recognition and basic interventions for babies who do not breathe at birth. HBB focuses on routine care after healthy birth, initial steps of helping the newborn to breathe at birth, ventilation with bag and mask, and ongoing care after resuscitation, with use of a simulator to practice these skills. Results of HBB field testing in Kenya, Pakistan and India demonstrated improved knowledge and skills in providers and helped refine the educational materials, which are currently in use in 55 countries.

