2	Facility in-charge or designated provider/pharmacist	Health facility assessment checklist;	Total: 3 (Baseline, Midline, Endline)
2 and 3	Providers in health facilities who attend births on days and are present on days of training and/or assessment/observation [Population: providers who attend births]	Written knowledge tests and OSCE competency tests for BAB and HBB using simulators	Before and after BAB training Before and after HBB training day Midline assessment Endline assessment Total: 4
		Direct Clinical Observation (DCO) of births at facility	Total: 3 (Baseline, Midline, Endline); providers may be observed several times over the course of the 2 or 3 day assessments
3, 4	Women giving birth in health facilities on days of observation, and newborns [Population: women giving birth and their newborns]	Direct Clinical Observation (DCO) of births at facility	1 (women will likely be observed only with one birth over the period of the study)
4,5	All women who give birth in study facilities (and newborns) will have their service delivery statistics recorded (without identifiers) and aggregated	Abstraction from Facility registers (existing registers and supplemental information for the HMS:BAB and HBB project)	None
1, 2	Providers described above who are selected to be Peer Practice Coordinators (PPC) who attend births and are selected to be PPCs due to leadership skills [Population: see	PPC practice logs	Weekly, the PPC will record data in the practice log.

Obj.	Study Participants (Sample & Population)	Data Source	Number of Study Contacts
	above]		
1	Providers, Facility In-charges, and stakeholders such as Ministry of Health in-charges	Semi-structures interviews	1
1	Providers	Focus group discussions	1

b. Describe any screening procedures and any **inclusion or exclusion criteria**.

For Providers:

- **Inclusion Criteria:** Health providers who attend births in participating health facility and consent to be assessed at the time of enrollment and at several points in time over two years.
- **Exclusion Criteria:** none

For Peer Practice Coordinators:

- **Inclusion criteria:** criteria for being a PPC include: being an experienced skilled birth attendant and likely to remain at the facility during the study period
- **Exclusion Criteria:** Provider has <1 year of experience, and has plans to be transferred to another facility or leave the facility soon.

For Women in Labor and Delivery and Newborns - Observations of Births

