2) **Study procedures, including sequence and timing.**

Figure 1 presents an overview of activities related to the intervention and its evaluation.

Figure 1 – Intervention and Evaluation Activities

Saving Lives on the Day of Birth: Building and Sustaining Capacity of Frontline Health Workers in Uganda

Intervention Description – More Detailed

Intervention: Bleeding After Birth

The intervention starts with all study arms receiving a one-day, facility based PPH prevention simulator-assisted training of all providers who attend births in a facility with the simulators being left onsite for ongoing practice:

The first module of the twinned training, “Bleeding after Birth” (BAB), uses graphic materials and simulation, to teach providers psychomotor and decision making skills to prevent, detect, and manage PPH including both treatment and timely referral as appropriate. To ensure retention and improved performance, for two of the study arms training will be followed by ongoing **low dose, high frequency (LDHF) simulation practice** conducted by Peer Practice Coordinators at the facility. (The “training-only” study arm will have the PPH simulator left at the facility with a recommended schedule for practice, but no PPCs designated to coordinate the training.) PPCs will be providers already posted at the facility who have undergone the training and have agreed to take on the role to support ongoing training in their facilities. After the initial training module is delivered, two providers per facility will be invited to participate in improving care for PPH and newborns by become PPCs. Two will be selected to address turnover and ensure simulated practice is conducted on a routine basis. After training in the first module (BAB), the PPCs will undergo a half-day training to enhance their skills related to peer-led training.

To test the added value of **mobile phone support**, providers or PPCs in one of the two intervention arms receiving the PPC LDHF intervention will receive ongoing SMS and voice support during the LDHF practice period. PPCs will be provided ongoing mobile support as reminders for practice and to maintain their clinical and training-related capacities. This technology will be used to provide remote reinforcement, assessment and real-time performance support by master trainers to PPCs. In addition, SMS messaging will be used for providers in this intervention arm to provide clinical content and practice reminders.

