 - Designated Peer Practice Coordinators (PPC) will log their weekly practice sessions on logs (full and partial arms only).
 - Data on the number of reminders that are sent to providers will be recorded, along with logs of calls between trainers and PPCs (full arm only).
 - Aggregated HMIS data related to PPH, newborn care and mortality data will be collected from routine and supplemental HMIS forms.
- When the five months of the active intervention phase is over, then there will be a midline assessment of providers and facilities: this will again involve a facility assessment, provider knowledge test and OSCEs, observation of provider performance, and qualitative data collection at some facilities. This will take place over 2 or 3 days.
- During the same time period, the research team will contact stakeholders by telephone to schedule interviews with them. Then the interviews will be conducted at the stakeholders' offices or another location, if requested by the stakeholder.
- Following the midline assessment, there will be a 'dormant' phase of no active intervention. This is to determine if competencies and performance is maintained by low-dose high-frequency practice in the absence of donor support. We will return six months later for an endline assessment, which is the same as the midline assessment except there will be no qualitative component.

Table 7. – Description of Data Collection Instruments

Tool #	Title	Content
1	Health Worker Listing	Name and cadre for each health worker at each facility. This will be used to generate a unique ID for each provider
2	Facility Inventory	Information about the tools and equipment available at the facility related to the study intervention, such as the availability of uterotonic drugs and neonatal resuscitators.
3	Direct clinical observation tool	Structured checklist that observers will use to take notes on the care provided to women and neonates, including routine care and treatment for postpartum hemorrhage or neonatal asphyxia.
4	Supplemental maternity register	Note: We will provide this register to facilities, but Jhpiego researchers will not abstract individual records from this document (facility staff will do this). This register collects data about each birth that is relevant to this study, such as whether a woman was diagnosed with postpartum hemorrhage and whether a newborn received bag & mask resuscitation.

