5	Supplemental monthly summary report	This aggregated monthly form collects facility-level indicators related to this study, such as the number of women diagnosed with postpartum hemorrhage and the proportion of those women treated with oxytocin or misoprostol.
6	Participant Characteristics – Baseline	This self-administered questionnaire collects information about qualifications of training participants and their prior experience and confidence related to preventing and treating postpartum hemorrhage and neonatal asphyxia.
7	Knowledge Test: Bleeding	15 multiple choice questions that test providers' knowledge of the

Tool #	Title	Content
	after Birth	content taught in the Bleeding After Birth training.
8a-c	Observed Structured Clinical Examinations (OSCEs): Bleeding After Birth	Structured checklists that trainers will use to examine providers' skills related to routine care for third stage labor, retained placenta, and severe hemorrhage due to atony. Providers will demonstrate skills on a simulator.
9	Peer Practice Coordinators' Practice Log	In two of the study arms, peer practice coordinators will use this form to record when the providers at their facility practice with the simulator and the topic that they practice.
10	Phone Support for Peer Practice Coordinators	This will log the data and content of the weekly phone support that trainers have with peer practice coordinators (in one study arm only.)
11	Opt-in Sheet for Mobile Phone Reminders for Providers and PPCs	In one study arm, providers will have the option of receiving reminders about training content via their personal mobile phones.
12	Knowledge Test: Helping Babies Breathe	17 multiple choice questions related to the content taught in the Helping Babies Breathe training.
13 a, b	OSCEs: Helping Babies Breathe	Structured checklists that trainers will use to examine providers' skills related to neonatal resuscitation using stimulation and ventilation equipment. Providers will demonstrate skills on a simulator.
	Qualitative	
14	Focus group discussion guide	Health care providers will be asked about their experiences with the program, particularly what the factors that motivated or discouraged them from practicing with the simulator.
15	Semi-structured interview guide: Health facility in-charges	Health facility in-charges will be asked about their experiences implementing the program and for their opinions about how to strengthen and sustain it.

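### Objective 5b's PPH case fatality rate is undefined, and its apparent denominator, provider-diagnosed PPH, can be moved by the training itself, so a change over time need not reflect a change in deaths

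*Combined protocol and SAP*

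**What the plan says.** Section 1, Objective 5 (IMPACT): "Reduce over time: a) the percent of facility-based deliveries who experience PPH; b) the PPH-related case fatality rate". No numerator or denominator is given for the case fatality rate.

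Footnote 1, marked at the end of Objective 5 and so read here as covering 5a to 5c alike: "These rates or proportions may increase between baseline and midline due to better reporting". It then expects the intervention to bring a fall between midline and endline.

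Section 3a, Table 2, names facility registers, existing and supplemental, as the source for Objectives 4 and 5: "All women who give birth in study facilities (and newborns) will have their service delivery statistics recorded".

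Section 4b2, Table 7, describes the instruments by example. The supplemental maternity register (Tool 4), from which facility staff do the abstraction, holds items "such as whether a woman was diagnosed with postpartum hemorrhage and whether a newborn received bag & mask resuscitation". The monthly summary (Tool 5) holds indicators "such as the number of women diagnosed with postpartum hemorrhage and the proportion of those women treated with oxytocin or misoprostol". No blood-loss criterion or independent adjudication of PPH is described.

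Section 4b2, Intervention: Bleeding After Birth, says that the module is meant "to teach providers psychomotor and decision making skills to prevent, detect, and manage PPH".

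Section 4b5 plans GEE models for service delivery statistics, with time, study group and their interaction. It does not mention case detection and specifies no outcome of PPH deaths per delivery. Section 3c says that no sample size was calculated for these data.

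**The concern.** A case fatality rate is deaths divided by recognised cases. Here the people who recognise the cases are the people being trained to recognise them, and the study also supplies or modifies the registers in which they write them down. Better recognition mostly adds women who survive, so the rate falls. Successful prevention removes cases, and if those are mostly the less dangerous ones, the rate rises. Neither movement by itself says whether fewer women died.

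Footnote 1 does not resolve this. More complete case reporting raises 5a, as the footnote says. For 5b, more recorded non-fatal cases push the rate down. A reader who relies on the footnote could take an early fall in 5b as benefit achieved in spite of reporting drift, when reporting drift could have produced it.

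**Working it through.** The plan states no expected value, effect or power for 5b, so there is no figure to reproduce. The check is ratio arithmetic.

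**Inputs from section 2 (Background):** maternal mortality ratio 310 per 100,000 live births; about 34% of these deaths due to PPH; PPH incidence 10.8% globally and 25.7% in Africa; prevention of PPH by as much as 64%. **From section 3:** 133 facilities in districts averaging at least one birth per facility per day.

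**Assumptions:** the national ratio applies to births in these facilities; all PPH deaths are recorded; *s* is the share of non-fatal PPH that staff diagnose. The plan gives no value for *s*, so a range is shown.

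**Deaths.** 310 × 0.34 = 105.4 PPH deaths per 100,000 births.

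**Recorded rate.** With incidence *p*, births *B* and deaths *D*: rate = D / [D + s × (pB − D)].

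**1. Detection changes, no death averted** (B = 100,000, D = 105.4). At p = 10.8%, non-fatal cases number 10,800 − 105.4 = 10,694.6. For s = 0.30 the rate is 105.4 / (105.4 + 3,208.4) = 3.18%. For s = 0.60 it is 105.4 / (105.4 + 6,416.8) = 1.62%.

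| s before → after | Rate, p = 10.8% | Relative change | Relative change, p = 25.7% |
|---|---|---|---|
| 0.50 → 0.55 | 1.93% → 1.76% | −9% | −9% |
| 0.60 → 0.70 | 1.62% → 1.39% | −14% | −14% |
| 0.50 → 0.80 | 1.93% → 1.22% | −37% | −37% |
| 0.30 → 0.60 | 3.18% → 1.62% | −49% | −50% |

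The relative change hardly depends on the incidence used.

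**2. Prevention works, detection constant** (shown for complete detection, p = 10.8%; the falls in deaths are assumptions). The starting rate is 105.4 / 10,800 = 0.98%.

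- PPH down 64%, deaths down 30%: 73.8 / 3,888 = 1.90%, a rise of 94%, while 31.6 deaths per 100,000 births are averted.
- PPH down 64%, deaths down 50%: 52.7 / 3,888 = 1.36%, a rise of 39%.
- PPH down 30%, deaths down 15%: 89.6 / 7,560 = 1.19%, a rise of 21%.
- Deaths and cases down by the same proportion: no change.

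**3. Detection fades between midline and endline.** With s from 0.80 to 0.60 and deaths down 20% (84.3), the rate goes from 1.22% to 84.3 / (84.3 + 0.60 × 10,715.7) = 1.29%, a rise of 6% although deaths fell.

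**4. Deaths per delivery in the same scenarios.** Under scenario 1 it is 105.4 before and after. With deaths down 30% it goes from 105.4 to 73.8, whatever happens to the number of diagnosed cases.

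**5. Expected number of deaths.** 133 × 365 = 48,545 births a year; one third is 16,182 per arm, or 8,091 in six months. 8,091 × 0.001054 = 8.5 PPH deaths per arm, about 25.6 over the three arms. This assumes the caseload floor and equal arms.

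**The case against.** The strongest reply is that Objective 5 already holds the answer. If 5a and 5b use the same recorded cases, their product is PPH deaths per delivery: 3.31% × 3.18% and 6.52% × 1.62% both return about 105 per 100,000 in the last row of the table. That is true. It shows that the better measure is nearly free, but not that it is planned: the stated target is still a fall in 5b, and no model is fitted to the product.

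Several stronger readings that a reader might draw are not supported:

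- *That the bias always favours the intervention.* Footnote 1 places the claimed benefit between midline and endline, which is the dormant phase. If recognition fades then, the rate moves upward, against the intervention (scenario 3).
- *That a lower rate in the full arm is an artefact.* All three arms receive the same BAB training, so the initial shift is largely common to them, and the planned group-by-time interaction would largely remove it. A between-arm bias needs peer practice or reminders to change detection differently by arm, and the plan gives no figure for that.
- *That a halving is to be expected.* It needs detection roughly to double. Modest shifts give 9–14%.
- *That the plan states the denominator.* It does not. Provider diagnosis is inferred from example items in Tools 4 and 5, though no other source of PPH cases is named for Objective 5.
- *That footnote 1 is simply wrong.* It says only that rates may increase, and section 8d allows for separate death registers. If recording of PPH deaths improved proportionally more than recording of cases, 5b would rise. The plan does not say that it expects this.

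It is also fair that 5b has its own use, as survival given diagnosed PPH, and that a per-delivery rate is not free of bias: it depends on deaths being recorded and attributed to PPH, and the training in timely referral may shift deaths between facilities.

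**Conclusion.** The point holds in a limited form. As the instruments imply it, 5b cannot serve alone as evidence that PPH deaths changed over time. The direction of the effect follows from the ratio, given that deaths are recorded equally well throughout. Its size rests on the assumed detection shares, and the opposite movement rests on deaths falling proportionally less than cases or on recognition fading. The few expected deaths make any reading of PPH mortality uncertain whichever denominator is used. Because 5b is neither a primary outcome nor part of Hypotheses 1–4, this is a cheap improvement to an impact objective and does not threaten the study's main conclusions.

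**What to change.** 1. Add PPH-related maternal deaths per facility delivery as the impact measure for PPH mortality, with deliveries as the offset in the GEE already planned in section 4b5.
2. Define the case fatality rate: which cases, which deaths, and from which register. Keep it as a descriptive measure of survival given diagnosed PPH, and show its numerator, its denominator and 5a beside it at each time point and by arm.
3. Reword footnote 1 to say that better case reporting is expected to raise 5a but lower 5b, unless recording of PPH deaths improves proportionally more.

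The cost is wording and one further model. Delivery counts are already needed for 5a and PPH deaths for 5b, so no new data are required in principle. The downsides are a wide interval for the new rate and its continued reliance on how completely deaths are recorded and attributed to PPH. The report should state both.
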